2.4.4.2.5 ABR in the onset period

Analysis includes all bleeding episodes occurring in the onset period. The on-treatment and treatment policy efficacy analysis are repeated with this endpoint. Estimated mean ABR and its 95% CI are presented. No formal hypothesis testing is performed.

2.4.4.2.6 ABR in treatment period (Global protocol)

Analysis includes all bleeding episodes occurring in the fitusiran treatment period. The on-treatment and treatment policy efficacy analysis are repeated with this endpoint. Estimated mean ABR and its 95% CI are presented. No formal hypothesis testing is performed.

2.4.4.2.7 Annualized weight-adjusted consumption of factor/BPA

Factor/BPA dose will be recorded by the patient in the eDiary and reviewed by the Investigator (and Sponsor or delegate) for the study duration to assess on-demand factor/BPA usage, as treatment of breakthrough bleeding episodes as well as prophylaxis factor/BPA usage. Weight-adjusted factor/BPA usage will be calculated programmatically.

The annualized weight-adjusted factor/BPA consumption for both treating bleeds and prophylaxis purpose, number of factor/BPA injections per bleed/per participant, weight adjusted total dose per bleed/per participant, and results of patient-reported evaluation of effectiveness of treatment for each bleed (excellent, good, moderate or none) as assessed by both patient and caregiver (Blanchette, 2014) will be summarized for both factor/BPA prophylaxis period and fitusiran treatment period. Additional summary will be provided by bleed location, causality and severity. The compliance to the bleed management guideline will be summarized after Day 8 to the end of study.

2.4.4.3 Multiplicity issues

No multiplicity control is provided for this study

2.4.5 Analyses of safety data

General common rules

All safety analyses will be performed on the safety analysis set (SAS1 or SAS 2) as defined in [Section 2.3](#), unless otherwise specified, using the following common rules:

- Safety data in patients who do not belong to the safety analysis set (eg, entered factor or BPA prophylaxis period and not treated with fitusiran) are listed separately
- The baseline value for fitusiran prophylaxis period is defined as the last non-missing value before the first dose of fitusiran. The baseline value for factor or BPA prophylaxis period is defined as the last non-missing value before the enrollment date.
- For ECG measurements, which are taken in triplicate, the average of the last triplicate readings before first dose of fitusiran/enrollment date is used as baseline for fitusiran prophylaxis period/factor or BPA prophylaxis period.
- The potentially clinically significant abnormality (PCSA) values are defined as abnormal values considered medically important by the Sponsor according to predefined criteria/thresholds based on literature review and defined by the Sponsor for clinical laboratory tests and vital signs
- PCSA criteria determines which patients had at least 1 PCSA during each observation period (factor or BPA prophylaxis period and fitusiran prophylaxis period), taking into account all evaluations performed during each observation period, including nonscheduled or repeated evaluations. The number of all such patients is the numerator for the PCSA percentage in each observation period.
- The PCSA denominator for a given parameter is based on the number of patients assessed for that given parameter in each observation period on the safety analysis set. Number (%) of patients with at least 1 PCSA is summarized regardless of baseline PCSA status and also by baseline PCSA status by observation period.
- For quantitative safety parameters based on central laboratory/reading measurements, descriptive statistics are used to summarize results and change from baseline values by visit and observation period. Summaries include the endpoint value which is defined as the last non-missing post-baseline assessment on or before EOS/ET visit for fitusiran prophylaxis period and on or before the day before first dose date of fitusiran for factor/BPA prophylaxis period.
- The analysis of the safety variables is essentially descriptive and no systematic testing is planned.
- All safety values including unscheduled measurements are assigned to the appropriate safety analysis visit window defined in [Section 2.5.4](#).

2.4.5.1 Analyses of adverse events

Generalities

The focus of adverse event reporting is on treatment-emergent adverse events and pre-treatment adverse events. Adverse events occurring in the screening period are analyzed separately.

If an adverse event date/time of onset (occurrence, worsening, or becoming serious) is incomplete (missing time, day, month or year), an imputation algorithm is used to classify the adverse event as pretreatment and treatment-emergent. The algorithm for imputing date/time of onset is conservative and classifies an adverse event as treatment emergent unless there is definitive information to determine it is pretreatment or posttreatment. Details on classification of adverse events with missing or partial onset dates are provided in [Section 2.5.3](#).

AEs are summarized by observation period (factor/BPA prophylaxis period and fitusiran prophylaxis period) and by the numbers and percentages of patients reporting at least one AE, having at least one AE by primary System Organ Class (SOC) and Preferred Term (PT). A patient with multiple occurrences of an AE is counted only once in the respective AE category. Patients who report multiple occurrences of the same AE (preferred term) are classified according to the most related or most severe occurrence, respectively.

All AE summaries are presented (frequency counts and percentages) by system organ class and/or preferred term, unless specified otherwise. The SOC is presented by internationally agreed order and the preferred term is sorted within each SOC in decreasing order of frequency in fitusiran prophylaxis period.

Analysis of all adverse events

An overall summary of AEs includes the number and percentage of patients with any:

- AE
- AE assessed by the Investigator as related to study drug (fitusiran only, possibly related or definitely related)
- severe AE
- severe AE related to study drug
- serious AE (SAE)
- SAE related to study drug
- AE/SAE of special interest
- Study drug related AE/SAE of special interest
- AE/SAE leading to study drug discontinuation
- Study drug related AE/SAE leading to study drug discontinuation
- AE/SAE leading to study withdrawal

- Study drug related AE/SAE leading to study withdrawal
- SAE with a fatal outcome.
- AEs potentially consistent with COVID-19

The overall summary of AEs will also be provided by hemophilia type.

Tabulations by SOC and PT are produced for the following:

- AEs
- AEs by severity
- AEs by hemophilia type
- SAEs
- AEs related to study drug (fitusiran prophylaxis period only)
- AEs related to study drug by hemophilia type (fitusiran prophylaxis period only)
- SAEs related to study drug (fitusiran prophylaxis period only)
- SAEs related to study drug by hemophilia type (fitusiran prophylaxis period only)
- AESI
- AESI by hemophilia type
- AEs leading to study drug discontinuation (fitusiran prophylaxis period only)
- SAEs leading to study drug discontinuation (fitusiran prophylaxis period only)
- AESIs leading to study drug discontinuation (fitusiran prophylaxis period only)
- AEs leading to study withdrawal
- SAEs leading to study withdrawal
- AEs potentially consistent with COVID-19

COVID-19 infection will be identified based on the search on MedDRA SMQ COVID-19 (narrow).

Tabulations by PT in decreasing order of frequency in the fitusiran prophylaxis period are produced for the following:

- AEs
- AEs by hemophilia type
- SAEs
- AEs related to study drug (fitusiran prophylaxis period only)
- SAEs related to study drug (fitusiran prophylaxis period only)

All AEs collected are listed along with the information collected on those AEs, eg, AE relationship to study drug, AE outcome etc. AEs that are not treatment-emergent are flagged in the listings. By-patient listings will also be provided for the following: all patient deaths, all SAEs, and all AEs leading to study drug discontinuation or study withdrawal, all AEs leading to death, AEs potentially consistent with COVID-19.

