1 OVERVIEW AND INVESTIGATIONAL PLAN

1.1 STUDY DESIGN

This is a multicenter, multinational, open label, Phase 3 switching study designed to characterize the efficacy and safety of fitusiran in male patients, aged ≥ 12 years, with severe hemophilia A or B, previously receiving factor or bypassing agent (BPA) prophylaxis.

The study consists of 2 cohorts: Cohort A consists of patients with inhibitory antibodies to factor VIII or factor IX. Cohort B consists of patients without inhibitory antibodies to factor VIII or factor IX. A subgroup of Cohort A patients includes hemophilia B patients with inhibitory antibodies to factor IX who are not responding adequately to BPA prophylaxis treatment (historical annualized bleeding rate (ABR) ≥ 20) (see Inclusion Criteria in Section 5.1 of the study protocol).

The study has 3 periods defined by type of prophylaxis regimen:

- 6-month factor/BPA prophylaxis period in which patients continue their prestudy, regularly scheduled prophylaxis regimen with factor/BPAs.

The subgroup of Cohort A patients who are not responding adequately to BPA prophylaxis treatment do not participate in this 6-month BPA prophylaxis period and start to directly receive fitusiran (in the 1-month onset period described below) after the screening period.

- 1-month onset period in which patients receive first dose of fitusiran while continuing their factor/BPA prophylaxis for up to 7 days.
- 6-month fitusiran efficacy period in which patients receive fitusiran prophylaxis.

Together, the 1-month onset period and the 6-month fitusiran efficacy period constitute the fitusiran treatment period. An additional 6 months follow-up period for monitoring of AT levels is required for patients who do not enroll in the extension study after the fitusiran treatment period.

Given that the study design employed is a single treatment arm, with a switch from factor/BPA prophylaxis to fitusiran prophylaxis for each patient, the study is not blinded and no randomization is performed.

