A target joint is defined as a joint where 3 or more spontaneous bleeding episodes in a single joint within a consecutive 6-month period has occurred; where there has been ≤ 2 bleeding episodes in the joint within a consecutive 12-month period the joint is no longer considered a target joint.

Efficacy analysis will focus on observed data as collected, unless otherwise specified. Patients who discontinue study drug during the study will be strongly encouraged to continue study participation including the recording of bleeding episode data. Only bleeding episodes that are treated with BPA/factor will be included in the primary analysis of endpoints evaluating bleeding.

Annualized bleeding rate will be calculated as described in [Section 2.4.4.1.1](#).

Efficacy Period and factor/BPA prophylaxis Period

In the protocol, for the purpose of ABR calculation, the factor/BPA prophylaxis period and fitusiran “Onset Period”, “Efficacy Period” and “Treatment Period” are defined. The factor/BPA prophylaxis period is defined as the 6 months period before the first dose of fitusiran, during which patients continue their pre-study, regularly scheduled prophylaxis regimen with factor concentrates or BPAs. The Onset Period is defined as the first 28 days after the first dose of fitusiran, during which the AT lowering capacity of fitusiran is increasing but has not yet reached therapeutic levels. The Efficacy Period is defined as starting on Day 29 when the AT lowering capacity of fitusiran has achieved therapeutic target range. The Treatment Period is defined as the onset period plus the efficacy period. The window for each period is summarized in the table below.

Period	Definition
Factor/BPA prophylaxis period	Day -168 to the earlier of Day -1 or the last day of bleeding follow up
Fitusiran onset period	Day 1 to the earlier of Day 28 or the last day of bleeding follow up
Fitusiran efficacy period	Day 29 to the earlier of Day 190 or the last day of bleeding follow up
Fitusiran treatment period	Onset period plus the efficacy period

The last day of bleeding follow up is defined as the deactivation date captured in eDiary.

If a patient does not have bleeding episode data collected after Day 28 due to early study discontinuation in the fitusiran treatment period, the efficacy period will be from Day 1 to the earlier of date of study discontinuation and the last day of bleeding follow up.

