2.1.4 Safety endpoints

The safety analysis will be based on the reported adverse events (AEs) including SAEs and other safety information, such as clinical laboratory data, vital signs, weight and height, physical examination, ECG findings, and ADA detection/assessment.

Observation period:

- Factor/BPA prophylaxis period is defined as the time from enrollment (Month-6 visit) up to the 1st dose of fitusiran.
- Fitusiran prophylaxis period is defined as the time after the 1st dose of fitusiran up to the end of the study (defined as last protocol planned visit). It includes the following 2 periods:
 - Fitusiran treatment period is defined as the time after the 1st dose of fitusiran to the EOS/ET visit,
 - Follow up period is defined as the time after Fitusiran treatment period up to the end of the study.

The treatment-emergent adverse event period equals fitusiran prophylaxis period.

On-study observation period includes both factor/BPA prophylaxis period and fitusiran prophylaxis period.

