A supportive efficacy analysis will be performed for the primary endpoint by using the Bayesian repeated measure Negative Binomial regression model. The informative prior distributions of the model parameters (eg, treatment effect, random effect, dispersion) may be used in the model. The ratio of ABR in the fitusiran efficacy period (fitusiran treatment period for US protocol) to the factor/BPA prophylaxis period, its 95% CI and the posterior probability of clinically significant treatment effect will be estimated. To assess sensitivity of the posterior distribution to this informative prior, an additional analysis will be performed using a neutral prior assuming mean ABR ratio of 1.

This Bayesian analysis will be implemented via PROC MCMC in SAS.

Covid-19 related sensitivity analysis

To address the impact of Covid-19, the above on-treatment and treatment policy efficacy analyses will be repeated on the Covid-19 unaffected set as defined in [Section 2.3](#). In addition, a sensitivity analysis based on on-treatment strategy will be performed by excluding the additional following intercurrent events:

- Period of missing at least two fitusiran doses in consecutive scheduled visits due to Covid-19 which is defined as one month after last dose (ie, last dose date + 29 days) before missing doses due to Covid-19 to one month after starting of re-dosing (ie, first re-dose date + 28 days). For participants treated with fitusiran 50mg Q2M dose regimen, replace the number of 28 with 56.
- Period from 6 months after enrollment of factor/BPA prophylaxis period to the date of first fitusiran dose if the date of first fitusiran dose was delayed due to Covid-19

The same negative binomial model as in the primary analysis will be used.

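### Adverse-event percentages are tabulated for observation periods of unequal length without exposure adjustment, so the fitusiran column can read higher at equal risk

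*SAP*

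**What the plan says.** SAP 2.4.5.1 sets the format of the adverse-event (AE) tables: "AEs are summarized by observation period (factor/BPA prophylaxis period and fitusiran prophylaxis period) and by the numbers and percentages of patients". Repeat events do not add to the count: "A patient with multiple occurrences of an AE is counted only once in the respective AE category".

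SAP 2.1.4 defines the two periods. On the control side, "Factor/BPA prophylaxis period is defined as the time from enrollment (Month-6 visit) up to the 1st dose of fitusiran". On the other side, "Fitusiran prophylaxis period is defined as the time after the 1st dose of fitusiran up to the end of the study". The SAP splits that second span into a treatment part ending at the EOS/ET visit and a follow-up part after it. The AE tables use the whole span, because "The treatment-emergent adverse event period equals fitusiran prophylaxis period". SAP 1.1 gives the length of the follow-up part: "An additional 6 months follow-up period for monitoring of AT levels is required for patients who do not enroll in the extension study".

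The efficacy definition of the prophylaxis period in SAP 2.1.3.1 has the same nominal length: "Day -168 to the earlier of Day -1 or the last day of bleeding follow up". The end of the safety period can move, because it is tied to the actual first dose. A Covid-19 sensitivity analysis in SAP 2.4.4.1.2 anticipates this by setting aside the stretch from six months after enrolment "to the date of first fitusiran dose if the date of first fitusiran dose was delayed due to Covid-19".

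SAP 2.4.5 describes the safety analysis as essentially descriptive, with no systematic testing. SAP 2.4.3 summarises study duration by period but does not use it as a denominator for AEs. SAP 2.4.5.2 plans Kaplan-Meier curves for first ALT and AST above 3 × ULN. Neither SAP 2.4.5.1 nor Protocol 8.2.8 plans a person-time rate or an equal-window table for AEs.

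**The concern.** A percentage of patients with at least one event is a cumulative incidence. It rises with observation time even when the underlying risk is constant. If the two columns of a table cover different lengths of time, the longer one shows more patients with events at equal risk.

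The SAP deals with this elsewhere. The bleeding-rate model offsets for each patient's duration in each period (SAP 2.4.4.1.1). Deaths are separated into those on fitusiran treatment and those in follow-up (SAP 2.1.4.2). The endpoint value for quantitative safety parameters in the fitusiran prophylaxis period is taken on or before EOS/ET (SAP 2.4.5). The AE tables have no equivalent.

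Characterising safety and tolerability is a secondary objective. With no testing planned, the by-period tables are where a reader will look for an excess of thrombosis, cholecystitis or cholelithiasis. As planned, they cannot separate a true excess from longer observation. This cuts both ways: an artefact may be read as harm, and a real excess may be put down to the longer window. The tables of potentially clinically significant abnormalities and of ALT/AST categories by observation period share the feature.

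**Working it through.** **Inputs from the documents**
- Screening runs from Day -228 to Day -169, and Month -6 is Day -168 (Protocol Table 1).
- The EOS/ET visit is Day 197 ± 7 (Protocol Table 1).
- AT follow-up adds six months for patients not entering the extension (SAP 1.1).
- Total time on study is up to 15 months with rollover and up to 21 months without (Protocol 4.2).

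**Assumptions, not in the documents**
- The event hazard is constant and equal in both periods.
- The incidence over 168 days is p, ranged from 5% to 50%.
- The share of patients who do not roll over is ranged from 0 to 100%.

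**1. Reproduce the stated durations.** Screening is 60 days, about 2 months. Then 2 + 6 + 7 = 15 months, and 15 + 6 = 21 months. Both stated figures are reproduced, so the period lengths are read correctly.

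**2. Period lengths and ratios**
- Prophylaxis: 168 days nominal.
- Fitusiran, rollover: 197 days, ratio 197/168 = 1.17 (1.13 to 1.21 over Day 190 to 204).
- Fitusiran, no rollover, full follow-up: 197 + 168 = 365 days with 28-day months (ratio 2.17), or 197 + 183 = 380 days with calendar months (ratio 2.26).
- If the six months were instead counted from the last scheduled dose on Day 169: 169 + 168 = 337 days (ratio 2.01).

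**3. Incidence at equal risk.** Over d days the incidence is 1 − (1 − p)^(d/168).

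| p over 168 days | 197 days | 365 days | 380 days |
|---|---|---|---|
| 5% | 5.8% | 10.5% | 11.0% |
| 10% | 11.6% | 20.5% | 21.2% |
| 30% | 34.2% | 53.9% | 55.4% |
| 50% | 55.6% | 77.8% | 79.2% |

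**4. What the table would show.** The tabulated percentage is a mixture. With share s not rolling over and staying 380 days, and p = 10%, it is (1 − s) × 11.6% + s × 21.2%.
- s = 0: 11.6%
- s = 25%: 14.0%
- s = 50%: 16.4%
- s = 100%: 21.2%

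For a cohort of about 50 patients, such as Cohort B, the excess over 10% is 0.8 patients at s = 0 (1.6% × 50), 2.0 at s = 25% (4.0% × 50) and 5.6 at s = 100% (11.2% × 50).

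**5. Delayed first dose.** The gap for rollover patients closes when the prophylaxis period reaches 197 days, a delay of 197 − 168 = 29 days. A longer delay reverses it for them: with 228 days of prophylaxis the ratio is 197/228 = 0.86.

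**6. After adjustment.** The first-event rate is −ln(1 − p)/168 × 365.25 × 100 per 100 patient-years. For p = 10% this is 22.9, for 30% it is 77.5 and for 50% it is 150.7. At equal risk each value is the same in both periods, so the rate ratio is 1.00 whatever the window lengths.

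**The case against.** The case against has real weight.

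**Safety is not framed as a comparison.** The safety objective lacks the phrase about factor or BPA prophylaxis that qualifies several other secondary objectives, and nothing is tested. Tables of drug-related AEs and of AEs leading to drug discontinuation cover the fitusiran period only. This stands, and it is why no error rate is at stake. The general AE, SAE and AESI tables are still produced by period.

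**Some time information is planned.** A reader might infer that every AESI, including the liver ones, is left with crude percentages. That is not so: ALT/AST above 3 × ULN is an AESI and has Kaplan-Meier curves, deaths are split at EOS/ET, and durations are summarised. An overall duration table does not, however, let a reader adjust a given SAE or AESI percentage.

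**The bias is conservative, and the long window has a purpose.** At constant risk the longer window works against fitusiran, and follow-up covers time when AT may still be lowered. Both points are fair. Neither helps a reader who must decide whether an observed excess is real.

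**Two stronger readings are tempting.** The first is that fitusiran percentages are roughly doubled. The documents do not support that for a cohort. It needs every patient to decline or miss the extension and to use the full six months, whereas Protocol Table 1 lets follow-up end when AT returns to about 60% or at investigator discretion. The second is that patients who stop for poor tolerability are watched longest. Those who stop early but stay may recover AT sooner, and those who leave altogether have EOS/ET assessments targeted within four weeks of the last dose (Protocol 5.3.2). The longest windows could belong to completers who do not enter the extension. Window length may vary with tolerability, but the documents do not show in which direction.

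**Conclusion.** The point holds as a reporting weakness that should be corrected. On planned durations the fitusiran AE window is about 1.17 times the prophylaxis window for rollover patients, and up to 2.17 to 2.26 times for non-rollover patients who use the full follow-up. The likely distortion is modest if most patients roll over and grows with the share who do not.

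The size rests on a constant, equal hazard, an assumed 10% base risk and an unknown rollover share. A hazard that falls during follow-up would shrink the excess. The 168 days are nominal, so delayed first doses would shrink or reverse the gap for rollover patients. Uncertainty about the actual window lengths is itself a reason to report rates per unit of time. The effect is confined to how descriptive safety tables are read.

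**What to change.** Keep the planned numbers and percentages, and add the following to SAP 2.4.5.1:

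- For AEs, SAEs and AESIs, by period: patients with a first event per 100 patient-years at risk (time censored at the first event), and events per 100 patient-years, with the patient-years shown.
- A treatment-emergent table cut at EOS/ET, which is the fitusiran treatment period already defined in SAP 2.1.4, with AT follow-up as a separate column.
- Rates for each segment separately. A single rate pooled over treatment and follow-up could be diluted by off-drug time.
- The number of patients entering AT follow-up and the distribution of its length.

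The cost is a few extra table columns and some programming from enrolment, first-dose, EOS/ET, last-follow-up and AE onset dates that are already collected. No new data or visits are needed.
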